5.1.7 Medical Record Review

Include a listing of the variables that will be abstracted from the medical chart (paper or electronic).

Date of birth Date of symptom onset Symptom complex at symptom onset Date of diagnosis Genotype MRI and CT findings Weight Height Head circumference Prior health events Prior and concomitant medications Level of baseline neurologic function (rolling, sitting, ambulation, speech etc).

5.1.8 Pregnancy Testing

A pregnancy test will be performed (if applicable).

5.2 Screening and Monitoring Evaluations: Performed as a Part of Research

5.2.1 Physical Examination

One complete physical examination (excluding pelvic and rectal examinations) will be performed at screening. This examination will determine whether the patient meets the criteria required to participate in the study and will also serve as a monitor for preexisting conditions and as a baseline for TEAE assessment. Body weight and height will also be recorded. Additional limited physical examinations will also be performed during the study (Study Schedule in Appendices 1 and 2). Fundoscopy may be completed as part of the physical exam if complaints of headache are present or irritability worsens on medication, and ophthalmology may be consulted as clinically indicated.

5.2.2 Vital Signs

Vital signs (blood pressure and pulse) will be measured at times indicated in the Study Schedule (Appendices 1 and 2). Any clinically significant findings that result in a diagnosis should be captured on the eCRF and reported as an AE. Additional measurements of vital signs may be performed at the discretion of the investigator.

5.2.3 Symptom Diaries

Symptom diaries are to be completed for at least two years from treatment initiation. Refer to Appendices 6 and 7 for symptom diaries.

5.2.4 AGS Scale

Refer to Appendix 5 for AGS Scale, which will be applied at baseline, 3 months, 6 months, 9 months, 12 months and every subsequent study visit through neurologic exam and conversation with parents.

5.2.5 GMFM-88

Individuals affected by AGS can have a range of motoric disability, secondary to direct muscle inflammation (myositis) as well as from injury to the central nervous system. The GMFM-88, administered by trained physiotherapists, covers 5 distinct categories: lying and rolling, sitting, crawling and kneeling, standing, and walking and running. Preliminary data demonstrates the feasibility of GMFM-88 in individuals affected by AGS (Figure 7). We will continue these serial assessments and compare the GMFM-88 scores to the clinical diaries, skin manifestations, and IFN signature scores, as described elsewhere.

Composite scores for the GMFM-88 will be calculated ^{25,46,66} and compared to normative data. Additionally, domain and subdomain scores will be recorded as raw and standardized scores. Functional measures developed for typically developing or mildly affected children (cerebral palsy) have not been validated in severe disorders such as AGS. However, our preliminary data suggests that these measures are reliable measures in AGS subjects.

The GMFM-88 may be performed remotely, via video assessment. The remote assessments will be performed by trained therapists that will administer the assessment and score the performance live, having the patients' parents assisting their children if needed according to a published, validated approach⁶⁷.

The families will be provided with information prior to the research encounter regarding the necessary environment and technology needed for home evaluations, as included in the following table:

Small bench smaller than 3' (feet touch floor when sitting)
Large bench to stand and cruise
12"-24" stick
Large object to carry with two hands (soccer ball or similar)
5 steps/rail
2 straight parallel lines 20' x ³ / ₄ ' and 20' x 8"
24" circle

Sessions will be conducted over a secure video conferencing platform (e.g.: Cisco WebEx/BlueJeans/myCHOP). Existing home equipment, including typical home furniture, will be selected to be as close as possible to the standard equipment and for subsequent evaluations and logged for consistency, in accordance with the GMFM-88 manual. All 88 items will be administered during the virtual encounter. Session will be recorded with a fixed camera angle.

5.2.6 AGS Development

In addition to formal measurement of motor function through the AGS scale and the GMFM-88, we will also employ descriptive approaches to assess typical developmental milestones. Progressive childhood diseases, such as AGS, offer unique complications in that they require the assessment of children with potentially worsening skills superimposed on an evolving panel of predicted developmental milestones. This scale allows for assessment of skills (smiling, head control, rolling) as compared to the average (P50) child affected by AGS, as opposed to age-matched controls (Figure 2). We will assess the longitudinal benefit of baricitinib on the rate of acquisition of skills in the domains of motor, speech and manual abilities. These scales can be applied using historical data acquired during clinical encounters with validated functional tools including the gross motor function classification system (GMFCS), manual ability classification system (MACS), communication function classification system (CFCS), and the Eating and Drinking Ability Classification system (EDACS) ⁶⁸.

5.2.7 Skin Inflammation

As one of the most clinically measurable manifestations of AGS is the dermatologic involvement, we have initiated a project to define and quantitate the skin manifestations found in patients with AGS. Aside from neurologic injury, skin manifestations are one of the most common manifestations of AGS, occurring in over 30% of affected individuals². As hypothesized, in our preliminarily results, the skin manifestations in AGS have been robustly responsive to baricitinib therapy (Figure 3).

Additional investigations will utilize the assessment tool CLASI (Cutaneous Lupus Erythematosus Disease Area and Severity Index) before and after treatment with JAK1/2 inhibitor. The dermatologic findings will be correlated with measures of neurologic function and the clinical diary as described above. The skin ulcerations and chilblains found in individuals affected by AGS are hypothesized to be secondary to an underlying vasculopathy ⁵⁷⁻⁵⁹. All AGS subjects will undergo a standardized dermatologic evaluation as well as the CLASI, a validated measurement instrument for skin disease (Cutaneous Lupus Erythematosus Disease Area and Severity Index)⁶⁰.

This scale has established content validity and reliability ^{60,69} and was developed in collaboration with our collaborator [name] who is experienced in its application and analysis. It has since been used extensively in clinical trials in SLE ^{39,40,70-73}, and appears responsive to treatment. These evaluations will be performed by 2 independent clinicians for each assessment. Any patient identified as having skin abnormalities (expected approximately 30% ³) will be referred for a full dermatologic evaluation.

5.2.8 Cardiac monitoring

Pulmonary hypertension (PH) is a rare but potentially fatal disorder characterized by severe vasculopathy and elevated pulmonary artery pressures leading to right-sided heart failure. Progressive PH has both genetic and inflammatory influences ²⁸⁻³⁴. In particular, type I interferons, as are overexpressed in AGS, have been established as risk factors for the development of PH ^{29,35-38}. We have identified several individuals within our cohort with PH, as related to systemic interferon overexpression (paper submitted). Cardiac involvement will be guantified using clinical assessment and echocardiogram. As per World Health Organization (WHO) guidelines, PH will be defined as persistently elevated mean pulmonary arterial pressure of ≥25 mmHg and a pulmonary capillary wedge pressure of \leq 15 mmHg for precapillary PH ⁶⁴. In setting of contraindication to cardiac catheterization (e.g. critical illness), combined echocardiographic and clinical evidence of PH will be utilized ⁶⁵. Individuals affected by AGS will have screening cardiac evaluations every other year. If not previously performed on a clinical basis, this may be performed on a research basis. In the patients identified as being affected by PH, we will follow the relationship between PH, and the response to baricitinib.

5.2.9 Electrocardiograms

Twelve-lead ECGs will be obtained clinically during the screening process. A single 12lead ECG measurement will be performed at screening. Subsequently, ECGs will be obtained every other year as a part of clinical care to screen for pulmonary hypertension, in addition to echocardiograms every other year as discussed above. If not previously performed on a clinical basis, this may be performed on a research basis.

5.2.10 Chest X-ray and tuberculosis screening

During the screening process, if no chest x-ray was done clinically within 6 months prior to the study, chest x-ray will be done as part of the research study. The chest x-ray will be reviewed by the investigator or his/her designee to exclude patients with active TB infection. In addition, patients will be tested at screening for evidence of active or latent TB as described above. If this has not been done clinically, in the context of standard of care, this will be done on a research basis.

5.2.11 Bone growth monitoring

Animal studies have elicited concerns about bone growth in juvenile animals. Height and weight will be monitored every 6 months. If patients are <1%, they will be referred to their local pediatric team for clinical management. Bone growth monitoring will be performed to include hand/wrist/fingers X-rays at baseline, 6 months, 12 months and then every 12 months as long as there are no radiographic concerns. The hand is placed on or up against a hard plate while a camera-like machine is placed opposite of the plate. This machine sends a very small burst of radiation which passes through the hand and creates images on the recording plate. IGF-1 will be completed yearly with safety labs. This will be completed on a research basis. With IGF-1 abnormalities, or radiographic concerns for accelerated bone growth, we will refer to bone health team for clinical monitoring.

Hand/wrist/fingers X-rays and IGF-1 testing will not be completed after a bone age demonstrating complete growth.

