6.2 Secondary Endpoints

Secondary endpoints will include the following:

- Improvement of the AGS scale from Screening to Treatment over time.
- Improvement of the GMFM-88 between Screening and Treatment over time.
- The change in Interferon Signaling gene score between Screening and Treatment over time.
- The change in skin symptoms between Screening and Treatment over time using the CLASI.
- Safety and tolerability of DRUG based on Adverse Events (including laboratory abnormalities).
- Change in AGS disease severity score (daily diary) between Screening and two years of treatment.

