6.3.5 Safety Analysis

All subjects entered into the study at Visit 1 will be included in the safety analysis. The frequencies of AEs by type, body system, severity and relationship to study drug will be summarized. SAEs (if any) will be described in detail. AE incidence will be summarized along with the corresponding exact binomial 95% two-sided confidence intervals.

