6.4 Sample Size and Power

Sample size calculations were performed using PASS 16 sample size software and were based on preliminary data in 35 patients with available data on the AGS scale.

Analysis of the primary outcome, safety data including laboratory studies and adverse events, will be descriptive and include all individuals, available studies and AEs. Power

analysis is not possible for these analyses, since adverse events may be rare, even in the AGS population, and statistical comparisons may not be feasible.

We anticipate that we will have an evaluable sample size of ~45 treated patients. For the analysis of secondary outcomes, in our preliminary analysis when we compared the average of AGS scales prior to treatment (pre-treatment average) to the average of the AGS scale after treatment (post-treatment average), we observed that the average of within subject changes (post-treatment average minus pre-treatment average) was 0.80 (95% CI = 0.45, 1.16) and that the standard deviation of changes was 1.04. This corresponds to an effect-size of 0.80/1.04 = 0.77. From PASS 16, a sample size of 30 data pairs achieves 98.3% power to reject the null hypothesis of zero effect size when the population effect size is 0.77 and the significance level (alpha) is 0.050 using a twosided paired t-test. Should the effect-size be smaller than we observed in our preliminary data, we will have 80% power to detect an effect size of 0.53, which would correspond to an average of within subject changes of 0.55, if the SD of changes is 1.04. We will therefore have sufficient power to detect differences that are similar to those observed in preliminary data. For the more complex analyses that are proposed for the larger data set that contains the historical controls (>50), our power will be even greater.

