9.4.2.1.7 Bone growth

During a juvenile rat study completed to support the dosing of baricitinib to patients 1 to <12 years, there were reductions in overall growth evidenced by lower body weights. Additional skeletal effects were observed in the juvenile rat study including marginal-to slight decreases in femur and tibia size as well as an apparent acceleration of normal maturation ossification centers. These findings were not associated with premature closure of growth plates or other functional consequences. Microscopically, there was a focal increase in trabecular bone. The effects of baricitinib in the pediatric population is not characterized. In addition, it should be noted that children with AGS have decreased overall growth which is assumed to be related to their chronic inflammatory disease.

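### Height, weight and bone age are collected because of a juvenile-animal growth signal, but Section 6 plans no analysis of them, so growth is monitored for care and not evaluated

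*Combined protocol and SAP*

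**What the plan says.** Section 5.2.11 gives animal findings as the reason for growth monitoring. Height and weight are checked every 6 months, with one rule: "If patients are <1%, they will be referred to their local pediatric team for clinical management". No reference chart, change from baseline or growth velocity is named. The section also schedules hand, wrist and finger films (baseline, 6 and 12 months, then yearly) and yearly IGF-1. An abnormal IGF-1, or a film suggesting accelerated bone growth, leads to a bone health referral. Films and IGF-1 stop once bone age shows growth is complete.

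Section 9.4.2.1.7 describes the rat findings: lower body weight, slightly smaller femur and tibia, and earlier maturation of ossification centers. It says paediatric effects are not characterised and adds that "children with AGS have decreased overall growth which is assumed to be related to their chronic inflammatory disease".

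In Section 6:
- The safety endpoint in 6.2 is "Safety and tolerability of DRUG based on Adverse Events (including laboratory abnormalities".
- Section 6.3.5 says "The frequencies of AEs by type, body system, severity and relationship to study drug will be summarized", with exact binomial intervals for incidence.
- Section 6.4 calls the safety analysis descriptive and names laboratory studies and adverse events.
- The change-from-baseline summaries with 95% CI in 6.3.1 are for primary and secondary outcomes, and growth is neither.
- The historical cohort (3.1.3) is for the AGS scale.

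**The concern.** The trial may treat growing children for up to 288 weeks, with a named preclinical growth signal. It gathers the measurements that bear on that signal but has no plan to summarise them. Gradual loss of height-for-age seldom presents as a discrete event, so a table of adverse events is likely to miss it.

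The <1% rule does not fill the gap. It looks at attained size and not at change. It flags a child who was already very small from AGS before the first dose, and it is silent on a child who drifts down on drug but stays above the line. The report could then be reassuring while children lose ground, or could raise a concern that predates treatment.

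The protocol accepts the same reasoning elsewhere. For liver enzymes, 5.2.12.1 notes that about one-third of patients are abnormal at baseline, so standard metrics are hard to apply, and it looks for rises from the patient's own baseline.

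**Working it through.** **The plan's own figure.** There is none for growth. The only power statement, in 6.4, is for the AGS scale: "a sample size of 30 data pairs achieves 98.3% power to reject the null hypothesis of zero effect size", at effect size 0.77. A two-sided paired t-test with df = 29 and noncentrality 0.77 × √30 = 4.22 gives 98.27%; at effect size 0.53 it gives 80.1%. Both reproduce the stated 98.3% and 80%, but they say nothing about growth. What carries over is the sample size: 30 pairs, and about 45 evaluable treated patients.

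**Inputs not in the documents (assumptions).** <1% is read as the 1st percentile of a reference chart. Baseline height z is taken as normal with mean μ from 0 to -2.5 and SD 1. The SD of within-child change in z, s, is taken as 0.6 to 1.0.

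**Step 1: what the cut-off detects.** The cut is c = Φ⁻¹(0.01) = -2.326. A child at the median must lose 2.33 SD to reach it. A child at the 25th percentile (z = -0.674) must lose 2.326 - 0.674 = 1.65 SD.

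Share below before any dose: p0 = Φ(c - μ). After every child loses δ: p1 = Φ(c - μ + δ). Newly flagged: p1 - p0. For μ = -1 and δ = 0.5: p0 = Φ(-1.326) = 9.2%, p1 = Φ(-0.826) = 20.4%, newly flagged 11.2%.

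| Mean baseline z | Below before any dose | Newly below after 0.5 SD loss | Newly below after 1 SD loss |
|---|---|---|---|
| 0 | 1.0% | 2.4% | 8.2% |
| -1 | 9.2% | 11.2% | 28.0% |
| -1.5 | 20.4% | 16.8% | 36.5% |
| -2 | 37.2% | 19.7% | 37.8% |
| -2.5 | 56.9% | 18.1% | 31.1% |

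So a loss of 0.5 SD in every child raises no new flag in about 80% to 98% of them. Letting the baseline SD run from 1.0 to 1.3 with means of -1 to -2, 9% to 40% are below the line at baseline, and 25% to 63% are still above it after a 1 SD loss.

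**Step 2: what a within-child analysis would give.** The 95% half-width is t(0.975, n-1) × s/√n.
- n = 45, t = 2.015: 2.015 × 0.6/6.708 = 0.18; with s = 1.0, 0.30.
- n = 30, t = 2.045: 2.045 × 0.6/5.477 = 0.22; with s = 1.0, 0.37.

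The mean loss detectable with 80% power is 0.427s at n = 45 (0.26 to 0.43 SD) and 0.529s at n = 30 (0.32 to 0.53 SD).

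**Step 3: are the data there?** Appendix 2 marks height and weight at every visit, including screening, and schedules the hand films. Sections 5.1.7 and 5.2.15 list weight and height among the variables taken from the medical record. Section 5.2.11 says every 6 months and Appendix 2 says every visit, which should be reconciled. Some required visits may be by telephone without a physical examination (Appendix 2, footnote p), so usable measurements will be fewer than the grid suggests.

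**The case against.** The strongest reply is that <1% is only a prompt to refer a child for care. A reader might infer from 5.2.11 that it is how the trial judges growth harm; no section says so. It is also not the only trigger: films and IGF-1 have their own, and the film trigger is aimed at the accelerated-ossification part of the animal signal. That is right, and the point here does not depend on the cut-off being wrong.

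A reader might also infer that the trial yields nothing but referrals, or that growth data will never be looked at. The text does not go that far. IGF-1 is a listed laboratory test and falls within the laboratory safety summary. Recognised slowing of growth could be recorded as an adverse event. The wording on safety data in 6.4 is not exhaustive. The DSMB reviews interim safety data under a charter that is not in these documents. What stands is narrower: no analysis of height, weight or bone age is prespecified.

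Finally, growth is not a stated endpoint, there is one arm, and a falling mean z-score could be disease or drug. This limits what an added analysis can show. It does not justify omitting a description of data collected for this very reason.

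**Conclusion.** The point holds as a gap in the analysis plan. Height, weight and hand films are collected because of a juvenile-animal signal, and Section 6 specifies no analysis of height, weight or bone age. As planned, the signal is monitored for care and not evaluated.

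A stronger conclusion, that the trial is unable to address the signal, is not supported. The measurements are scheduled and could be analysed without new procedures. Equally, the added analysis would not settle causation.

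The sizes above are illustrations, because the documents give no growth z-scores or SDs. The figure of 45 is an upper guide. Eligibility has no upper age limit, patients who have finished growing contribute nothing, and some visits are by telephone, so fewer than about 45 growing patients will have on-site measurements. The change is worth making. It touches no efficacy conclusion.

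**What to change.** Add to 6.3.5 a descriptive growth analysis in patients who have not completed growth:
- Change from the last pre-dose value in age- and sex-standardised height and weight z-scores, over time, with 95% CI and a named reference chart.
- Comparison with each child's pre-treatment course where chart values exist.
- The share already <1% at baseline.
- Bone age minus chronological age at each scheduled film, for patients with a pre-dose film. Patients rolling over from the compassionate use study start this protocol already treated, so some may have none.

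State that the <1% rule is a referral for care and not the growth safety outcome. Whether that threshold should change is for the clinicians.

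State the limits with the result: one arm, so limited attribution to drug; incomplete pre-treatment records; measured height affected by scoliosis, hip dislocation or spasticity, which 8.4.1 lists as AGS complications; and fewer than about 45 growing patients with on-site measurements.

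The cost is one added safety analysis on data already scheduled, with no new procedure.

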5.2.12 Laboratory Evaluations

Appendix 2 lists the schedule for sample collections in this study. Appendix 8 lists the specific tests that will be performed for this study. The blood volume frequencies will not exceed the volumes permitted by the NIH (no more than 5 mL/kg may be drawn for research purposes in a single day and no more than 9.5 mL/kg may be drawn over any eight-week period for children, and no more than the lesser of 10.5 mL/kg or 550 mL may be drawn for research purposes over an 8-week period for adults).

In order to address constraints on blood volumes for laboratory tests in younger patients (<1 year), alternative methods of assessing baseline risk of hepatitis, HIV, or TB (e.g. testing of parent) may be considered, as well as limited PK studies. If not previously performed on a clinical basis, this may be performed on a research basis.

5.2.12.1 Samples for Standard Laboratory Testing

Blood and urine samples will be collected at the times specified in the Study Schedule (Appendices 1 and 2). Standard laboratory tests, including chemistry, hematology, and urinalysis panels, will be performed. Every effort should be made to obtain all laboratory tests listed in Appendix 8. Missing laboratory testing will be reported in aggregate to the IRB during continuing reviews. The blood volume frequencies will not exceed the volumes permitted by the NIH.

Standard age based pediatric norms will be used to assess out of range values for laboratory testing.

Additional blood samples may be drawn if needed for safety purposes and/or if warranted. Investigators must document their review of each laboratory safety report.

Liver-Function Monitoring

Liver-function monitoring will occur frequently throughout the study. It should be noted that approximately one-third of individuals with AGS have elevations of AST and ALT that are consistent with hepatitis at baseline (AST and ALT fold increase of 3 times and GGT fold increase of 2.5 times from upper limit of normal). Thus, use of standard metrics such as the Recommended Hepatic Evaluation Guidance Document are difficult to apply in this population. If elevations in ALT/AST or total bilirubin occur from the patient's baseline, the patient should be closely observed in consultation with study staff with expertise in hepatology and the Management of Liver Enzyme Laboratory Values (Appendix 9).

Other safety monitoring

Other clinical safety testing, including CBC, renal function and infectious testing will be discussed with study team and the clinical care providers.

